7.2 Statistical Methods

The primary analysis will be conducted to determine the presence and expression levels of 800 miRNA's among DCIS and invasive breast cancer patients. Based on the resulting profiles, we will determine whether or not its expression for each miRNA from the tumor side differs from that of the normal side.

We will interrogate 800 miRNAs. The vast majority will not be expressed in any sample. A minority will be measurable/detectable in some samples and a smaller minority will be detectable in all samples.

The presence of miRNA can be as follows:

- a. Present in tumor and absent in normal
- b. Present in normal and absent in tumor
- c. Present at high level in tumor and low level in normal
- d. Present at high level in normal side and low level in tumor.

Of these a and c are most important and relevant for our analysis. If even a single miRNA is absent in tumor and present in 30% of cancers or if there is at least one miRNA out of these 800 that is present at low levels in all "normals" and high levels in 30% of tumors that would be a "success". We will dichotomize to low and high levels of miRNA to calculate frequencies and the associated risk estimates and 95% confidence intervals. The comparison of proportions will be performed using two-sample z-tests.

CONFIDENTIAL

This material is the property of [name]. Do not disclose or use except as authorized in writing by the study sponsor

7.3 *Subject Population(s) for Analysis*

Patients diagnosed with DCIS or invasive breast cancer.

8 Safety and Adverse Events

8.1 *Definitions*

Adverse Event

An ***adverse event*** (AE) is any symptom, sign, illness or experience that develops or worsens in severity during the course of the study. Intercurrent illnesses or injuries should be regarded as adverse events. Abnormal results of diagnostic procedures are considered to be adverse events if the abnormality:

- results in study withdrawal
- is associated with a serious adverse event
- is associated with clinical signs or symptoms
- leads to additional treatment or to further diagnostic tests
- is considered by the investigator to be of clinical significance

Serious Adverse Event

Adverse events are classified as serious or non-serious. A ***serious adverse event*** is any AE that is:

- fatal
- life-threatening
- requires or prolongs hospital stay
- results in persistent or significant disability or incapacity
- a congenital anomaly or birth defect
- an important medical event

Important medical events are those that may not be immediately life threatening, but are clearly of major clinical significance. They may jeopardize the subject, and may require intervention to prevent one of the other serious outcomes noted above. For example, drug overdose or abuse, a seizure that did not result in in-patient hospitalization, or intensive treatment of bronchospasm in an emergency department would typically be considered serious.

All adverse events that do not meet any of the criteria for serious should be regarded as ***non-serious adverse events***.

Adverse Event Reporting Period

The study period during which adverse events must be reported is normally defined as the period from the initiation of any study procedures to the end of the study treatment follow-up. For this study, due to the short half life of oxytocin, the study treatment follow-up period for adverse event reporting will be considered completed at the Visit 2/End of Study visit as outlined in Protocol Section 6.2.

Preexisting Condition

A preexisting condition is one that is present at the start of the study. A preexisting condition should be recorded as an adverse event if the frequency, intensity, or the character of the condition worsens during the study period.

CONFIDENTIAL

This material is the property of [name]. Do not disclose or use except as authorized in writing by the study sponsor

General Physical Examination Findings

At screening, any clinically significant abnormality should be recorded as a preexisting condition. At the end of the study, any new clinically significant findings/abnormalities that meet the definition of an adverse event must also be recorded and documented as an adverse event.

Post-study Adverse Event

All unresolved, oxytocin related adverse events should be followed by the investigator until the events are resolved, the subject is lost to follow-up, or the adverse event is otherwise explained. At the last scheduled visit, the investigator should instruct each subject to report any subsequent event(s) that the subject, or the subject's personal physician, believes might reasonably be related to participation in this study. The investigator should notify the study sponsor of any death or adverse event occurring at any time after a subject has discontinued or terminated study participation that may reasonably be related to this study. The sponsor should also be notified if the investigator should become aware of the development of cancer or of a congenital anomaly in a subsequently conceived offspring of a subject that has participated in this study.

Abnormal Laboratory Values

A clinical laboratory abnormality should be documented as an adverse event if any one of the following conditions is met:

- The laboratory abnormality is not otherwise refuted by a repeat test to confirm the abnormality
- The abnormality suggests a disease and/or organ toxicity
- The abnormality is of a degree that requires active management; e.g. change of dose, discontinuation of the drug, more frequent follow-up assessments, further diagnostic investigation, etc.

Hospitalization, Prolonged Hospitalization or Surgery

Any adverse event that results in hospitalization or prolonged hospitalization should be documented and reported as a serious adverse event unless specifically instructed otherwise in this protocol. Any condition responsible for surgery should be documented as an adverse event if the condition meets the criteria for an adverse event.

Neither the condition, hospitalization, prolonged hospitalization, nor surgery are reported as an adverse event in the following circumstances:

- Hospitalization or prolonged hospitalization for diagnostic or elective surgical procedures for a preexisting condition. Surgery should **not** be reported as an outcome of an adverse event if the purpose of the surgery was elective or diagnostic and the outcome was uneventful.
- Hospitalization or prolonged hospitalization required to allow efficacy measurement for the study.
- Hospitalization or prolonged hospitalization for therapy of the target disease of the study, unless it is a worsening or increase in frequency of hospital admissions as judged by the clinical investigator.

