Our aim is to first demonstrate proof of principle. We would like to extend our initial trial by 1 year since the NAF volumes were inadequate without pharmacologic enhancement. Specifically, we were able to collect NAF from 13/40 patients, of which 8 were successfully analyzed for miR. To remedy this problem, we propose collecting additional specimens in the setting of intranasal oxytocin. This project will establish a foundation from which future miR analysis may be completed.

3 Study Design

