5.2 Treatment Regimen

The Principal Investigator will administer one spray of intranasal oxytocin, or 4 IU, into each nostril approximately 15-30 minutes before NAF collection. Prior to collection, the nipples will be scrubbed with alcohol swabs to eliminate keratin plugs, breasts will be massaged by the MD investigator for approximately 2 minutes, but no more than approximately 7 minutes. An aspirator will be applied to each breast, and fluid will be collected into capillary tubes. NAF samples will be acquired from study subjects by the MD investigator in the operating room while under anesthesia before the opening incision. The duration of time required to obtain NAF samples will be documented.

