7.1 Sample Size Consideration

Contralateral breast without disease will serve as the control. In a sample of 40 patients with unilateral disease, we expect 60% of the patients to show significantly altered expression of miRNAs in the diseased breast as compared to the breast without disease for the test to be of clinical relevance. Ideally a detectable difference would be the difference between a null hypothesis of 0% and an alternative of 60% or a second alternative of 35%. Since this study is the first of its kind, we will consider the test to be not clinically relevant if less than 35% of patients show significantly altered expression miRNA in the diseased breast as compared to the breast without disease.

Using a two sample z-test, type I error of 0.05, and a two-sided significance level, a sample size of 40 will have greater than 80% power to detect a difference between a null hypothesis of 35% and an alternative hypothesis of 60%.

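### Section 7.2 calls an miRNA present or absent without reference to how much fluid or RNA each breast gave, so unequal yield could imitate a tumor signal; how often that becomes a success depends on a rule that contradicts itself

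*Combined protocol and SAP*

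**What the plan says.** Section 7.1 makes the comparison a within-woman one: "Contralateral breast without disease will serve as the control". Sections 3.1 and 6.1 describe NAF as coming from both breasts. No other specimen is explicitly taken from both sides, so the tumor-versus-normal comparison rests on NAF.

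Section 7.2 lists four patterns by side. Pattern (a) is "Present in tumor and absent in normal", (b) is its mirror image, and (c) and (d) are the high/low equivalents. It then states: "Of these a and c are most important and relevant for our analysis". Success can rest on one miRNA out of 800, and the first clause of the rule reads "If even a single miRNA is absent in tumor and present in 30% of cancers". The parallel clause, on levels, requires a low level in every normal sample. The named test is unpaired: "The comparison of proportions will be performed using two-sample z-tests".

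Section 7.2 expects detection to vary between samples: "A minority will be measurable/detectable in some samples and a smaller minority will be detectable in all samples". It gives no detection limit, minimum volume, RNA input, normalization, or rule for a breast with little or no fluid. Section 7.3 does not require an analysable pair. Sections 3.1 and 6.1 name the array and the software only.

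On yield, Sections 1.1 and 2 report from the phase without oxytocin that "we were able to collect NAF from 13/40 patients, of which 8 were successfully analyzed for miR". Section 2 expects adequate fluid from both breasts in 77% of women. The secondary endpoint in Section 3.3 concerns NAF volume, but has no figure and does not gate the miRNA calls. Section 5.2 says that "breasts will be massaged by the MD investigator for approximately 2 minutes, but no more than approximately 7 minutes" and has the collection time documented. It does not mention volume or RNA per breast.

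**The concern.** Whether a scarce miRNA is detected can depend on how much material was assayed. If one breast of a pair supplies less, miRNAs near the detection limit drop out together on that side. When that side is the normal breast, the result is pattern (a), the direction that counts towards success, with identical biology in both breasts. A dry or failed normal breast scored as absent would add to this.

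At stake is the reading of the tumor-versus-normal result: a difference in yield could be taken for a candidate marker. If volume and RNA are not recorded by breast at surgery, the two explanations may be impossible to separate afterwards.

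**Working it through.** The plan gives no figure for this point, and the power statement in 7.1 does not enter the check.

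**Inputs from the protocol**
- Earlier yield (1.1, 2): 13/40 = 32.5% collected; 8/13 = 61.5% of those analysed.
- Expected pairs (2): 0.77 × 40 = 30.8, about 31, leaving about 9 women without an adequate pair.
- 30% rule (7.2): 0.30 × 31 = 9.3, so at least 10 of 31; 0.30 × 40 = 12.
- Spread (1.4): volume increase of 1.39 ± 2.2 µL, so CV = 2.2/1.39 = 1.58 and log-SD = √ln(1 + 1.58²) = 1.12. This is a before-after increase in nine volunteers, used as a stand-in for volume spread.

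**Assumptions, not in the documents:** tumor-to-normal median volume ratio 1 to 3; between-breast correlation 0.5 (also 0 and 0.8); the same concentration in both breasts; woman-to-woman log-SD 1.0; assay log-SD 0.3; 100 miRNAs spaced evenly from −3 to +3 log units around the detection limit.

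**Check 1: simulation with no tumor effect, 31 pairs.** An miRNA is detected when log concentration + log volume + noise exceeds the limit. False success means that any miRNA meets the rule. Correlation is 0.5.

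| Volume ratio | Pattern (a) in ≥10 of 31 pairs | Present in ≥10 tumor sides, absent in all normals |
|---|---|---|
| 1 | 7% | 0% |
| 1.5 | 48% | 0.2% |
| 2 | 85% | 1% |
| 3 | 99% | 8% |

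Repeat runs move the larger pairwise figures by up to about 3 points. With independent volumes, the pairwise column is about 35%, 74%, 94% and 99.8%, and the all-normals column about 0%, 0.7%, 1.7% and 10%. With equal medians and correlation 0.8, the pairwise figure is 0.2%. With identical input on both sides it is 0% in this model.

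**Check 2: a count model for one miRNA.** P(detect) = 1 − exp(−λ × yield), with λ the assumed mean detectable copies on the tumor side and tumor-side yield set to 1.
- Normal side at half yield, λ = 1: detection 63.2% versus 39.3%. Pattern (a) = 0.632 × (1 − 0.393) = 38.3%; (b) = 0.393 × (1 − 0.632) = 14.5%. P(at least 12 of 40 show (a)) = 90%; at least 10 of 31, 81%. At λ = 2 and 3 the 12-of-40 figure is 65% and 12%.
- Normal side at 0.75 of the yield: 55%, 7% and 0.04% at λ = 1, 2 and 3.
- Equal yield, λ = 1: (a) = (b) = 0.632 × 0.368 = 23.3%. The direction disappears, but P(at least 12 of 40 show (a)) is still 20%.

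So equal input and a paired test do different jobs. At half yield and λ = 1, the share of discordant pairs that are (a) is 0.383/(0.383 + 0.145) = 73%, not 50%, so a paired test alone would carry the yield bias. Equal input alone leaves the chance successes.

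**Check 3: dry normal breasts scored as absent.** For an miRNA always present in tumor-side fluid, P(at least 12 of 40 show (a)) is 9%, 19%, 56% and 93% when 20%, 23%, 30% and 40% of normal breasts are dry. The 23% is 100% − 77% and would require every woman without an adequate pair to be dry on the normal side only.

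**The case against.** The strongest objection is that the large figures depend on one reading of the success rule. Section 7.2 does not say that pattern (a) is counted pair by pair. Its first clause cannot be satisfied as written, and its parallel clause refers to all normal samples. If absence in all normals is meant, false success is rare up to a two-fold difference. This stands, and both readings must be shown.

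A reader might infer that the normal breast is the drier one, so that the trial will report volume as a marker. The documents do not support this: no figure compares the sides. If yields differ only at random, (a) and (b) rise equally, although only the tumor-high direction is emphasized. The spread is borrowed from a different quantity, and pairs already adequate on both sides should vary less than an untruncated lognormal.

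A reader might also infer that dry breasts are to be scored absent, or that massage will differ within a woman. The plan says neither. The earlier report separates collected from successfully analysed samples, which leans towards treating failures as not analysed. It gives no cause for the five failures. Section 5.2 sets one range for both breasts and merely leaves inequality open.

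The array procedure may fix RNA input and the software may normalize. The plan states neither, and normalization cannot recover a signal below detection. Finally, this is a proof-of-principle pilot with a feasibility endpoint. That limits the consequences, but 7.2 still defines a success criterion on these calls.

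**Conclusion.** The concern holds as a conditional risk. Section 7.2 makes presence calls and emphasizes the tumor-high direction without linking them to per-breast yield, in a study whose own figures show yield to be limiting. Unequal yield can therefore produce pattern (a) without a tumor effect.

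Its size cannot be fixed from the documents. Under the assumptions above (log-SD 1.12, correlation 0.5, 31 pairs), false success runs from about 7% to 99% over volume ratios 1 to 3 on the pairwise reading, and from about 0% to 8% if absence in all normals is required. Until the contradictory clause is corrected, neither column can be called the trial's error rate.

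It would also go too far to conclude that equal RNA input settles the matter. The 0% in the simulation follows from its small assumed assay noise; the count model leaves 20% for a single miRNA.

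**What to change.** **First, in 7.2,** correct the success sentence and state whether pattern (a) is counted within pairs or requires absence in all normal breasts.

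**Then, in 7.2:**
- Include a woman in the tumor-versus-normal NAF comparison only if both sides pass the array quality check. A dry, insufficient or failed side is missing, never absent.
- Use equal RNA input within a pair where feasible, set by the smaller sample. Otherwise accept a pattern-(a) or pattern-(c) marker only if it persists in pairs whose volume or RNA ratio lies within a prespecified band (for example 2-fold).
- Compare (a) against (b) with a paired test in place of the two-sample z-test, with multiplicity control. The Study Summary names the Benjamini-Hochberg procedure, but for a comparison with a normative reference population, and 7.2 does not carry it over.

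**In 5.2:** apply the same collection procedure and duration to both breasts of a woman, alternate whether the tumor or normal side is collected first, and record volume, RNA yield and the already documented collection time per breast.

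**Cost:** protocol wording and a few recorded values per breast. Pairs with one failed side drop out, and some low-abundance miRNAs are lost on the richer side. Symmetric collection must fit the commitment in 3.1 and 6.1 not to prolong surgery.

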1.5 Dose Rationale and Risk/Benefits

Based on prior studies in non-lactating women, we plan to administer one spray (4 IU) per nostril 15-30 minutes before NAF collection. The benefits will be greater NAF yield for miR analysis. The risks include rare anaphylactic reactions, common headache, tachycardia or bradycardia, uncommon arrhythmia, very rare hypertension, common nausea and vomiting, rare rash and allergic dermatitis, and uncommon abnormal uterine contractions. Because of the possibility of abnormal uterine contractions, pregnant women will be excluded in the study. [Frequency: *Very common* (> 1/10); *common* (> 1/100 to < 1/10); *uncommon* (> 1/1000 to < 1/100); *rare* (> 1/10 000 to < 1/1000); *very rare* (< 1/10 000), including isolated cases.]

2 Study Objectives

The main objective of this study is to demonstrate the feasibility of characterizing miR profiles in the NAF, serum and tissue of patients with DCIS or invasive breast cancer. Each set of miRs will be assessed for correlation with tumor presence. Tissue and serum are expected to be acquired from all patients. With the addition of intranasal oxytocin, bilateral NAF collection of adequate volume for analysis is expected from 77% of participants at increased risk for breast cancer.¹⁶

Analysis of the miR profiles will include comparisons among the different biological samples (tissue, serum, NAF) in order to understand their relationships with one another. We hypothesize that cancer subtypes will be identifiable by unique miR fingerprints, with the goal of creating a breast cancer screening tool.

²⁸ Pedersen, Cort A., and David L. Penn. "Oxytocin Treatment of Social Cognitive and Functional Deficits in Schizophrenia - Full Text View - ClinicalTrials.gov." *Oxytocin Treatment of Social Cognitive and Functional Deficits in Schizophrenia - Full Text View - ClinicalTrials.gov*. National Institute of Mental Health, n.d. Web. <<http://clinicaltrials.gov/ct2/show/NCT01394471>>.

²⁹ Guastella, Adam J., Stewart L. Einfeld, Kylie M. Gray, Nicole J. Rinehart, Bruce J. Tonge, Timothy J. Lambert, and Ian B. Hickie. "Intranasal Oxytocin Improves Emotion Recognition for Youth with Autism Spectrum Disorders." *Biological Psychiatry* 67.7 (2010): 692-694.

³⁰ Simeon, D., J. Bartz, H. Hamilton, S. Crystal, A. Braun, S. Ketay, and E. Hollander. "Oxytocin Administration Attenuates Stress Reactivity in Borderline Personality Disorder: A Pilot Study." *Psychoneuroendocrinology* 36.9 (2011): 1418-421.

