3.2 Primary Study Endpoints

The primary endpoint is feasible miR analysis of NAF as well as serum and tissue collected from study participants.

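### Limb 1 of the 7.2 success rule contradicts itself and no miRNA can meet it; it should state pattern a, say which breasts count as normal, and be fixed before data are seen

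*Combined protocol and SAP*

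**What the plan says.** Section 7.2 lists four patterns, a to d, for a miRNA on the tumor and normal sides. Pattern a is "Present in tumor and absent in normal"; b is its mirror image; c is high in tumor and low in normal; d is the reverse of c. The text continues: "Of these a and c are most important and relevant for our analysis".

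Success is then defined by two alternatives, called limb 1 and limb 2 here. Limb 1 is "If even a single miRNA is absent in tumor and present in 30% of cancers". Limb 2 is "at least one miRNA out of these 800 that is present at low levels in all" normals and at high levels in 30% of tumors. The next sentence adds: "We will dichotomize to low and high levels of miRNA to calculate frequencies".

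Three other places bear on the rule:
- Section 7.1: "Contralateral breast without disease will serve as the control".
- The Statistical Methodology row of the Study Summary compares miRs with a normative reference population.
- Section 3.2: "The primary endpoint is feasible miR analysis of NAF", together with serum and tissue.

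**The concern.** Limb 1 puts absence and presence on the same side and places no condition on the normal breast. It occupies the position where pattern a belongs, and a is one of the two patterns that the plan says matter most.

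Correcting the wrong word leaves a choice open. Limb 2 refers to all normals, whereas 7.1 makes each patient's other breast her own control. A repaired limb 1 could therefore require absence in every normal breast, or only in the paired breast of each patient counted. The Study Summary even allows a third meaning, an outside reference population. Because one miRNA out of 800 is enough, a reading chosen after the data are seen could decide whether limb 1 is met.

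**Working it through.** **Inputs from the documents.** 40 patients, 20 with DCIS and 20 with invasive cancer (3.1), all taken as the denominator; 800 miRNAs and a 30% threshold (7.2). Section 2 says "bilateral NAF collection of adequate volume for analysis is expected from 77% of participants" at increased risk, which is used only as a sensitivity case. The plan gives no operating figure for this rule, so there is none to reproduce. The power statement in 7.1 concerns a different quantity, the share of patients with altered expression.

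**Step 1: limb 1 as printed.** The threshold is 0.30 × 40 = 12 patients. A miRNA absent in tumor is present in 0 of 40 cancers. Since 0 < 12 for every miRNA, 0 of 800 can qualify. The documents define no difference between tumor and cancers that would rescue the text.

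**Step 2: which pattern was meant.** Limb 2 is pattern c. The preceding sentence singles out a and c, so limb 1 should be a. Reading it as b, the only listed pattern with absence in tumor, would contradict that sentence.

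**Step 3: an example that needs no model.** Take a miRNA present in 20 of 40 tumors and 1 of 40 normal breasts. Under all normals it fails limb 1. Under pairing it has 19 or 20 qualifying patients (47.5% or 50%) against a cut of 12, and passes.

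**Step 4: a useful miRNA.** Let p be its tumor frequency and q its detection rate in normal breasts. Assume p = 0.40 and independent breasts; the documents give neither p nor q.
- All normals: P(Bin(40, p) ≥ 12) × (1 − q)^40
- Paired: P(Bin(40, p(1 − q)) ≥ 12)

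For q = 0.02: 0.929 × 0.98^40 = 0.929 × 0.446 = 0.414, against P(Bin(40, 0.392) ≥ 12) = 0.914.

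| q | All normals | Paired |
|---|---|---|
| 0 | 93% | 93% |
| 1% | 62% | 92% |
| 2% | 41% | 91% |
| 5% | 12% | 89% |

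At q = 2%, changing p to 0.30 gives 25% against 53%, and p = 0.50 gives 44% against over 99%.

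**Step 5: an uninformative miRNA.** Assume the same detection rate q on both sides, with independence between breasts and between miRNAs.
- Paired, per miRNA: P(Bin(40, q(1 − q)) ≥ 12) = 0.019, 0.117 and 0.285 at q = 0.2, 0.3 and 0.5. Among 50 such miRNAs, the chance of at least one false success is 1 − (1 − 0.0194)^50 = 63% at q = 0.2, then 99.8% and over 99.9%. At q = 0.1 it is only 0.7%.
- All normals, per miRNA: the maximum over q of P(Bin(40, q) ≥ 12) × (1 − q)^40 is 0.000018, near q = 0.16. Among 800: 1 − (1 − 0.000018)^800 = 1.4%.

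**Step 6: fewer evaluable pairs.** 0.77 × 40 = 30.8, about 31, and 0.30 × 31 = 9.3, so the cut is 10. The useful miRNA at q = 1%, 2% and 5% passes 63%, 46% and 17% of the time under all normals, against 85%, 84% and 80% paired. False success is at most 6.8% among 800 under all normals, against 62% to over 99.9% among 50 paired (q = 0.2 to 0.5).

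**The case against.** The strongest reply is that limb 1 contains a one-word slip that any analyst would correct from the preceding sentence, so the literal count of 0 in 800 describes a rule nobody would apply. That stands: the intended word is recoverable from 7.2 before any data. The choice of reading is less fully recoverable. Limb 2 points to all normals, while 7.1 points to the paired control.

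A reader might infer that the two readings would reverse the study's verdict. The documents do not support this in general. Success needs only one miRNA through either limb, so the verdict changes only if no other miRNA meets limb 1 and limb 2 also fails. If five independent markers like the one in step 4 existed, all normals would succeed on limb 1 in 1 − (1 − 0.622)^5 = 99%, 93% or 47% of studies at q = 1%, 2% or 5%. The gap narrows greatly at low q, but not at 5%.

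Independence between a woman's two breasts is also doubtful. If every detected normal breast belonged to a woman whose tumor side was also positive, the paired figure at q = 5% would fall from 89% to P(Bin(40, 0.35) ≥ 12) = 79%. Such concordance would also lower the paired false-success figures. The direction in step 4 holds; the exact sizes are illustrative.

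It is also tempting to say that 7.2 is silent on undetected miRNAs. That goes too far: the a to d list separates absent from low level, and only the later dichotomy into low and high raises doubt.

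**Conclusion.** The concern holds as a defect in limb 1. As printed it cannot be met, and that conclusion needs no assumption. Once repaired to pattern a, the all-normals and paired readings differ in both directions: all normals loses useful markers that are occasionally detected in normal breasts, and pairing admits many more chance findings. For a rule satisfied by a single miRNA, control of false success favors all normals, which is also the wording of limb 2. The probabilities rest on assumed p, q, independence and a count of 50 uninformative miRNAs. They describe limb 1 only and are not probabilities of study success.

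A reader might infer that the whole success rule is void or that the trial's main conclusion is at risk. Neither follows. Limb 2 can still be met, and the primary endpoint is feasibility. Nor is this the plan's only decision criterion: 7.1 separately sets a 35% relevance threshold on patients with altered expression, which neither replaces nor clarifies limb 1.

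**What to change.** Replace limb 1 in 7.2 with: *absent in all normal (contralateral) breasts and present in at least 30% of cancers*. In the same line:
- Declare that 30% is read as at least 30% (12 of 40); the present text does not say so.
- State that normals are the study patients' contralateral breasts (7.1), not the normative reference population of the Study Summary.
- If the per-patient paired reading is intended, say that instead, before data are seen.

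Optionally, add a clause saying whether an undetected miRNA counts as low when levels are dichotomized.

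The cost is a line or two of text. Sample size and specimen collection do not change, and the 30% figure stays, with its direction made explicit. The trade-off is that, under all normals, one detection in any normal breast defeats limb 1 for that miRNA.
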